2.0 BACKGROUND

This study aims to identify biomarkers that stratify Oncology patients on immune check point inhibitor (ICPI) that have an increased risk of developing autoimmune toxicity known as immune-related adverse events (irAE).

ICPIs are being increasingly prescribed and 10% of NHS Oncology patients receive treatment from this drug group (1,2). The reported rate of total irAE triggered by ICPI varies but is thought to be between 40-66% (3-5), a third of which are endocrine related (6,7).

Several bodies including the European Society for Medical Oncology, American Society for Clinical Oncology and the National Comprehensive Cancer Network have produced guidance for irAE management, but no unified screening protocol exists to stratify patients at high-risk (8). Currently the literature primarily centres around looking for prognostic biomarkers for treatment success rather than characterising toxicity.

Individual studies review the utilisation of some routine clinical blood tests, i.e., albumin, rheumatoid factor, lactate dehydrogenase, IL-6, etc, to screen and stratify high-risk patients (9,10). However, these tests are used in isolation and no singular clinical algorithm using a variety of routine tests has been developed for initial screening during ICPI therapy. A variety of protocols have been developed for screening endocrine irAE, although these are not consistently adopted, and practice varies.

ICPIs induce an enhanced immunological response to promote anti-tumour activity (11). There are a few forms of ICPI including CTLA-4 antibodies that upregulate T-cell activation pathways to enhance the tumour immune response. There are also antibodies that act as programmed death receptor agonists, which promote cytokine release and T-cell activation. (12)

An array of studies has shown that reactive oxygen species (ROS) are involved in the regulation of T-cell anti-tumour immunity (13–20). ICPI are active therapies that alter T-cell intracellular signalling, which can increase ROS production and proinflammatory cytokine secretion, thus exerting an immunotherapeutic effect (13).

irAE refers to a spectrum of autoimmune toxicities triggered by ICPI. ROS are implicated in the initiation, amplification, pathogenesis of autoimmune diseases (21,22). Are ROS heavily upregulated in irAE due to a dysregulated immune response and could the measurement of an oxidative stress marker act as a marker of toxicity?

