3.0 Objectives and Outcomes Measures/Endpoints

3.1 Primary objectives

Can a clinical algorithm be created to flag high risk Oncology patients that have a greater risk of developing irAE? In addition, can novel biomarkers such as malondialdehyde be incorporated into this algorithm to aid stratification.

- P Oncology adult patients on ICPI
- I No intervention – retrospective analysis
- C Comparing blood test results of those who develop irAE to those who don't
- O Are any of the blood tests significantly different in those who develop irAE
- T 6 months follow up post starting treatment, 18 testing period.

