3.2 Secondary objectives

This principal research question will be broken down to the following sub aims:

1. Are there any established biochemistry, haematology and immunology blood tests that produce significantly different results in those who develop irAE when compared to those that don't. Including IL-6 (requires in-house verification). Observational study
2. Can a malondialdehyde LC-MS/MS assay suitable for clinical laboratory use be developed based on a method development by Sobsey *et al.*
3. Is malondialdehyde significantly raised in those who develop irAEs compared to those that do not. An ELISA kit has been located in the event an LC-MS/MS method is not successfully developed.
4. Can a blood test clinical algorithm be developed to stratify patients at high-risk of developing an irAE.

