4.0 STUDY DESIGN

4.1 SUMMARY OF DESIGN

This is a retrospective cohort study that looks at blood test results correlated to clinical outcomes.

Oncology patients, whom have been prescribed ICPIs for the first time, will be identified via the chemotherapy scheduling system. This study does not require extra blood draws or tubes to be taken. Left over serum and plasma from routine clinical blood draws will be retrieved. This serum and plasma will be aliquoted into tube labelled with a pseudonym reference. The samples will be booked into our laboratory information management system under a pseudonym reference. This system is password protected and only those involved in this research should be accessing these records. Left-over samples will be frozen at -80C and stored for a period of 1 month before being tested in batches. Before testing a list of NHS numbers of the patients that have been recruited will be sent to the Trust's data office. All samples for patients that have opted out of having their records used for research purposes will be destroyed in line with local pathology policy. Once testing is completed the left-over samples will be disposed of as in line with the Human Tissue Act, 2004 and local Portsmouth Pathology protocols.

[name] lead researcher will correlate the results to the patients' identifiers in a password protected sheet. Results will then be clinically correlated to patient's records to deem patient outcomes and if they had an irAE. Data will be correlated into a password protected excel sheet kept on Trust computer system. Data will then be de-identified and patient identification will be removed. Identifiable patient data will be removed for data analysis the spread sheet would contain age in years, sex, cancer type, ICPI type, if they had an irAE, irAE type and when it occurred. This data will be in a password protected excel sheet. Statistics will be carried out via R.

Minimal patient data will be used in the write up of this study i.e., age in years, sex, cancer type, ICPI treatment type, and if they had an irAE. Information about irAE will include type of event, and when it occurred post treatment.

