4.2 ELIGIBILITY CRITERIA

Inclusion criteria

- ≥ 18 years of age
- All sex
- Oncology patients
- Who is prescribed FDA approved check point inhibitors: (ipilimumab, nivolumab, pembrolizumab, cemiplimab, atezolizumab, avelumab, and durvalumab)

BIO-CHECKPOINT

- All cancer subtypes are included

Exclusion criteria

- <18 years of age
- Those previously been treated with checkpoint inhibitors.
- Those with a previous medical history of autoimmune disease
- Those with previous medical history of endocrine diseases
- Those with a pre-existing malignancy
- Non-Queen Alexandra hospital oncology patients
- Lacking capacity to consent

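### The section 4.1 field list has no disease stage, treatment intent or performance status, so the planned analysis cannot show whether a blood test predicts irAE beyond known clinical status

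*Combined protocol and SAP*

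**What the plan says.** Section 4.1 describes the de-identified analysis file: "the spread sheet would contain age in years, sex, cancer type, ICPI type, if they had an irAE, irAE type and when it occurred". For the paper itself the same section says that "Minimal patient data will be used in the write up of this study" and gives a similar short list. Neither list has stage, treatment intent or performance status. The three items do not appear elsewhere in the visible protocol as eligibility limits, data items or covariates.

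On the population, section 4.2 says "All cancer subtypes are included" and names seven eligible drugs. None of the exclusions is by stage, intent or fitness.

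On the analysis, section 3.1 gives "Comparing blood test results of those who develop irAE to those who don't". Section 3.2 repeats this for established blood tests including IL-6 (sub-aim 1) and for malondialdehyde (sub-aim 3), then asks for an algorithm (sub-aim 4). Section 4.1 says that R will be used. No model or covariate is given.

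On the tests, section 2.0 cites other studies of "albumin, rheumatoid factor, lactate dehydrogenase, IL-6, etc, to screen and stratify high-risk patients". It also says: "Currently the literature primarily centres around looking for prognostic biomarkers for treatment success rather than characterising toxicity".

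On use, section 3.3 aims to flag patients before therapy starts, and section 13.0 aims for an orderable panel for all ICPI patients.

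**The concern.** Disease extent and fitness are known before treatment without a study blood test. If they shift a blood marker and also change the chance of a recorded irAE within 6 months, the marker will differ between the two groups even if it carries no information of its own. The unadjusted comparison would report that difference, and the algorithm could include the test.

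Cancer type and ICPI type are only partial stand-ins: nothing in section 4.2 stops two patients with the same cancer and drug from differing in stage or treatment intent.

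The protocol itself suggests one route to the outcome. Sections 1.0 and 3.3 say that irAE symptoms overlap with those of the malignancy, so disease extent could affect what is recorded as an irAE.

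At stake is the panel in section 13.0. It could contain tests that tell the oncologist nothing new, and the study would have no planned result to show otherwise.

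**Working it through.** **The plan's own figure.** Section 7.0 gives a minimum of 47 patients (irAE rate 40%, alpha 0.05, power 80%) but no effect size, SD, test or sidedness, so 47 cannot be verified. Several unstated inputs would produce it, for example a correlation of 0.4 tested two-sided: ((1.96 + 0.84)/atanh 0.4)² + 3 = (2.80/0.424)² + 3 ≈ 47. The present point does not depend on this figure.

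**Inputs from the documents.** Expected N 120, minimum 47, cap 150; irAE rate 40%; alpha 0.05 (all section 7.0).

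**Assumptions not in the documents.** 60% of patients have advanced disease; a marker is shifted by d = 0.5 to 1.0 SD in advanced disease and has no other link to irAE; advanced disease multiplies the odds of irAE by OR = 1 to 3; stage is recorded without error; tests are two-sided.

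**Step 1: stage-specific risks.** Each pair keeps the overall rate at 40%, that is 0.4 × p(not advanced) + 0.6 × p(advanced) = 0.40:
- OR 1.5: 0.342 and 0.438
- OR 2: 0.303 and 0.465
- OR 3: 0.25 and 0.50

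**Step 2: simulation.** 20,000 replicates per scenario compare an unadjusted t-test of irAE versus no irAE with the same comparison adjusted for stage. Chance of p < 0.05 at N = 120:

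| OR | d = 0.5 | d = 0.8 | d = 1.0 | Adjusted for stage |
|---|---|---|---|---|
| 1 | 5.4% | 5.3% | 4.9% | 4.7-5.3% |
| 1.5 | 5.9% | 6.4% | 7.2% | 4.9-5.5% |
| 2 | 7.3% | 9.9% | 11.8% | 4.8-5.2% |
| 3 | 9.7% | 16.9% | 21.9% | 4.8-5.2% |

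For OR 1.5 to 3 the unadjusted range is 5.2-10.9% at N = 47 and 5.8-26.9% at N = 150. The problem grows with N because it is a bias, so recruiting more patients does not cure it.

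**Step 3: hand check of the largest cell (OR 3, d = 1.0, N = 120).**
- Share advanced among irAE: 0.6 × 0.5/0.4 = 0.75. Among no irAE: 0.6 × 0.5/0.6 = 0.50.
- Expected marker difference: 1.0 × (0.75 - 0.50) = 0.25.
- Within-group variance: 1 + (0.4 × 0.75 × 0.25 + 0.6 × 0.50 × 0.50) = 1.225, so SD = 1.107.
- Standard error with 48 and 72 patients: 1.107 × √(1/48 + 1/72) = 0.206.
- Expected z: 0.25/0.206 = 1.21. P(Z > 1.96 - 1.21) ≈ 0.23, against 21.9% simulated.

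**Step 4: opposite direction.** A second simulation (4,000 replicates) had advanced disease lowering the risk: 75% advanced, irAE risk 35% versus 55%, OR (0.55/0.45)/(0.35/0.65) = 2.3. It gave 6.9-10.9% at N = 120, in line with the OR 2 row.

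**Step 5: room for an extra term.** Expected irAEs at 40%: 0.4 × 120 = 48; 0.4 × 47 ≈ 19; 0.4 × 150 = 60. One binary term is affordable at 120 and tight at 47.

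**The case against.** **A reader might infer that the gap can never be checked or repaired.** The documents do not support that. Records are opened to decide irAE status before identifiers are removed (section 4.1), the team can reverse the pseudonyms (section 6.1), linkage runs through the reference, and data are kept for a year after completion (section 6.3). The gap is in the planned dataset and analysis.

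**A reader might take albumin and LDH as study tests known to track disease extent.** Section 2.0 gives them only as examples from other studies. The objectives name IL-6 and malondialdehyde, with the established tests unspecified. No section says that any of these follows disease extent, or that extent changes irAE risk. Both links are assumptions and both are needed: at OR 1 there is no inflation.

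**A stage-driven difference is still a real difference.** This stands. It truthfully answers sub-aim 1 and can help to stratify risk. It is not a false finding in that sense; what remains untested is added value over clinical status.

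**Larger figures are tempting.** With irAE risks of 30% versus 63% (OR (0.63/0.37)/(0.30/0.70) = 4.0) and a 1 SD shift, one marker reaches 29% at N = 120. Nothing in the documents points to so strong a link. Counting any of three markers mixes in multiplicity: that rate is about 13% even after stage adjustment.

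**The list may be incomplete.** It omits the blood results, which the file must hold; the flow chart is not shown and the procedures cited in section 4.4 are not in the document. This weakens the inference of absence but does not remove it, since it is the only list of clinical fields given.

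**Minimal data is a stated choice.** That sentence concerns the write-up. It argues for few added fields, not for none.

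**Conclusion.** The point holds as one of untested added value. The stated field list lacks stage, treatment intent and performance status; eligibility does not restrict them; and the comparison is unadjusted. As written, the study cannot say whether a blood test predicts irAE beyond what disease extent and fitness already show.

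The size ranges from nothing to moderate. At 120 patients, a marker with no link to irAE beyond stage would be significant about 5% of the time at OR 1 and up to about 22% at OR 3 with a 1 SD shift. This assumes 60% advanced disease and that extent relates to both marker and outcome. The documents give no value for any of these, and the planned fields would not reveal which scenario applies. This is an inexpensive improvement to the design. It does not show that the planned comparison is invalid, or that any particular test is confounded.

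**What to change.** In section 4.1, add disease stage, treatment intent (adjuvant or neoadjuvant versus advanced) and performance status, all at ICPI start. Abstract them at the record review already planned for irAE status, before de-identification.

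In the analysis:
- Keep the unadjusted comparison.
- For sub-aims 1 and 3, add a pre-specified comparison adjusted for one binary stage/intent term, defined before results are linked to records.
- For sub-aim 4, fit a model with that term first and report whether the blood tests improve on it.
- Use performance status descriptively or in a sensitivity analysis.
- If recruitment ends near 47, label the adjusted results exploratory.

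The cost is two or three more fields per patient, a protocol amendment (to the Sponsor before the REC, section 17.1) and one degree of freedom. No new patients or samples are needed. A single binary term across all cancers is coarse, and adjustment will not correct progression misrecorded as an irAE, but about 48 expected irAEs leave little room for more terms.

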4.2 ELIGIBILITY CRITERIA

Inclusion criteria

- ≥ 18 years of age
- All sex
- Oncology patients
- Who is prescribed FDA approved check point inhibitors: (ipilimumab, nivolumab, pembrolizumab, cemiplimab, atezolizumab, avelumab, and durvalumab)

BIO-CHECKPOINT

- All cancer subtypes are included

Exclusion criteria

- <18 years of age
- Those previously been treated with checkpoint inhibitors.
- Those with a previous medical history of autoimmune disease
- Those with previous medical history of endocrine diseases
- Those with a pre-existing malignancy
- Non-Queen Alexandra hospital oncology patients
- Lacking capacity to consent

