Malondialdehyde is generated from ROS driven lipid peroxidation of polyunsaturated fatty acids and is an indirect marker of oxidative stress. Malondialdehyde can be detected within plasma, serum and urine via liquid-chromatography mass-spectrometry (LC-MS/MS). (23–25) Malondialdehyde has been suggested as a future marker of tissue level thyroid dysfunction, the most common irAE is hypothyroidism (26).

BIO-CHECKPOINT

At present, Portsmouth does not have a unified screening process for patients about to commence ICPI and tests requested are clinician dependent. This project seeks to produce a unified clinical algorithm.

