5.0 SAMPLE PROCESSING

5.1 SAMPLE COLLECTION AND STORAGE

Patients will be identified via the chemotherapy scheduling system, which will be reviewed and checked by lead researcher [name] daily Monday-Friday. Patients who are yet to start ICPI will be listed in a password protected sheet with the expected day of their chemo. The lead researcher will then check to assess that if the patients listed meet the inclusion criteria and if they have any of the features of the exclusion criteria. Those that meet the exclusion criteria will be deleted off the list. The laboratory information management system will be reviewed daily to assess if we have received their clinical bloods. Left over serum and plasma will be stored frozen and tested in batches once a month.

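### Existing endocrine or autoimmune disease is excluded by history only and an irAE need not be new since baseline, so a test that detects unrecognised disease could pass as a predictor; the size is unknown

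*Combined protocol and SAP*

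**What the plan says.** Two exclusions in section 4.2 bear on this: "Those with a previous medical history of autoimmune disease" and "Those with previous medical history of endocrine diseases". Both rest on what is already known about the patient. No blood result enters either of them.

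Section 5.1 has the lead researcher screen patients who have not yet started treatment against these criteria: "Those that meet the exclusion criteria will be deleted off the list". This happens before the stored sample is tested. Section 5.2 mentions an eligibility assessment around consent but describes no testing.

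On what would be known by then, section 2.0 says the site "does not have a unified screening process for patients about to commence ICPI and tests requested are clinician dependent".

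Sections 5.4 and 9.0 keep the study results away from clinicians and unlinked to records until May 2025. Section 4.1 then determines from the records whether each patient had an irAE. It gives no definition of an irAE and does not require the event to be absent at baseline. Section 3.2 compares the blood results between patients with and without an irAE.

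Section 2.0 puts irAE incidence at 40-66%, "a third of which are endocrine related", and states that "the most common irAE is hypothyroidism".

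**The concern.** The exclusions look intended to keep existing disease from being mistaken for treatment toxicity. They can do so only for disease that someone has already found. A patient with unrecognised thyroid dysfunction has no history to exclude. The study's own result cannot remove that patient, because it is produced later and stays unlinked. If the clinic first measures thyroid function during treatment, old disease can enter the record as a hypothyroid irAE. The stored sample's abnormal value then sits in the irAE group.

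That association would be circular, because the test would be detecting disease already present. Section 3.3 aims at a panel that identifies high-risk patients before therapy starts, and section 13.0 would make a panel orderable for all ICPI patients. Detecting existing disease may be useful, but it is a different claim from predicting toxicity, and the plan as written could not separate the two.

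**Working it through.** **The plan's own figure.** The protocol gives no rate of unrecognised baseline disease, so there is nothing to reproduce. Its minimum sample size of 47 does not bear on this point.

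**Inputs from the protocol.** Expected N = 120 and irAE incidence 40-66% (section 7.0); one third of irAEs endocrine (section 2.0); significance level 0.05 (section 7.0).

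**Assumptions not in the protocol.**
- The number k of enrolled patients with unrecognised disease is 0, 2, 4 or 6 (6/120 = 5%).
- All k are abnormal on the test and all are later labelled irAE. This is the worst case.
- The other 120 - k patients have a 40% irAE rate, and 5% of them are abnormal by chance, unrelated to irAE.
- The stored sample is pre-treatment, as sections 3.3 and 5.1 imply.

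**Step 1: endocrine events expected.** 120 × 0.40 / 3 = 16; 120 × 0.66 / 3 = 26.4. If hidden cases come on top of these, as in the tables below, they are between 4/(26.4 + 4) = 13% and 6/(16 + 6) = 27% of endocrine events. If they are already inside the total, the range is 4/26.4 = 15% to 6/16 = 38%.

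**Step 2: Fisher's exact test with no background abnormality.** Rows are abnormal and normal; columns are irAE and no irAE.
- k = 3: [[3,0],[47,70]], p = 0.070
- k = 4: [[4,0],[46,70]], p = 0.028
- k = 6: [[6,0],[46,68]], p = 0.0056
- k = 6 with only 4 labelled irAE: [[4,2],[46,68]], p = 0.23

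**Step 3: the same test with about 5% background.** About 0.05 × 116 = 5.8 chance abnormal results are expected with k = 4, and 0.05 × 114 = 5.7 with k = 6. Take 6, with 2 among irAE patients and 4 among the rest.
- k = 4: [[6,4],[44,66]], p = 0.32
- k = 6: [[8,4],[44,64]], p = 0.12

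**Step 4: chance of a significant result, by simulation under the assumptions above.** The Fisher column uses the normal/abnormal split. The rank column uses a Mann-Whitney test on continuous values, with the hidden cases made extreme.

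| Hidden cases k | Fisher, p < 0.05 | Rank test, p < 0.05 |
|---|---|---|
| 0 | about 3% | 5% |
| 2 | about 8% | about 6% |
| 4 | about 22% | about 10% |
| 6 | about 46% | about 17% |

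If each hidden case has only a two-thirds chance of being labelled irAE, the Fisher figures for k = 4 and 6 fall to about 7% and 10%.

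**Step 5: endocrine irAE only.** The protocol does not specify this comparison, but section 4.1 records irAE type, so it could be made. A separate simulation (N = 120, total irAE rate held at 40%, otherwise the same worst case) compared endocrine irAE with no irAE. A null marker was significant in 38% of runs at 2% hidden disease and 91% at 5%, against 1.7% with none.

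**The case against.** The strongest reply is that the size is assumed at every step. The protocol gives no prevalence. It describes pre-treatment testing as varying by clinician, not as absent, so some patients will have baseline thyroid results in the same records used to judge irAE. It lists no analyte panel: sections 2.0 and 3.2 name albumin, rheumatoid factor, lactate dehydrogenase, IL-6 and malondialdehyde, but not thyroid function or glucose as study tests. Sections 3.1 and 3.2 ask whether results differ significantly and do not mention a normal/abnormal split, so the rank-test column may be the more relevant one. All of this stands, and it limits how large the effect can be said to be. It does not close the gap.

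A reader might infer from step 2 that four hidden cases are enough to produce a significant finding. That holds only if nobody else has an abnormal result and every hidden case is labelled irAE. With ordinary background abnormality, the expected tables in step 3 are not significant.

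A reader might also infer that the whole algorithm, or malondialdehyde, is compromised. The documents do not support that. The mechanism reaches only tests that reveal existing disease. Section 2.0 calls malondialdehyde a suggested marker of tissue thyroid dysfunction, which makes an effect on it possible but does not establish one.

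Finally, discarding the event of every patient who is out of range at baseline would go too far. A mild abnormality that truly worsens on treatment is a legitimate risk signal.

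**Conclusion.** The point holds as a gap in outcome definition and analysis. Followed as written, the protocol can enrol unrecognised disease, count it as an irAE, and credit the baseline test that detects it with prediction. The chance of a false finding at N = 120 runs from little above nominal with 2 hidden cases to about 22-46% (Fisher) or 10-17% (rank test) with 4 to 6. Those figures rest on an assumed number of hidden cases, full labelling as irAE and, for Fisher, 5% background abnormality. Partial labelling shrinks them, while an endocrine-only comparison would enlarge them. The autoimmune exclusion has the same form, but no autoimmune case has been quantified here.

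**What to change.** 1. In section 4.1, count an event as an irAE only if it is new or worsened relative to the pre-treatment results available, whether from the stored sample or the clinical record.
2. Before the irAE comparison, flag each patient whose pre-treatment result already shows the same abnormality. Report the comparison with and without flagged patients. Other irAEs in a flagged patient still count.
3. Include thyroid function and glucose in the batch where sample volume allows. The samples are leftovers and section 5.3 expects none to remain, so this is desirable but not a condition of items 1 and 2. The decision has to be made before testing, because any remainder is destroyed afterwards and baseline status could not then be recovered for patients the clinic did not test.

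The cost is one definition, one extra column in the data sheet, one sensitivity analysis and possibly two routine assays. No extra blood is needed, and clinicians still do not see the results. The downside is a few fewer endocrine events in the sensitivity analysis. Unrecognised autoimmune disease is covered only as far as the tests actually run can show it.

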3.3 Outcome

This project could produce a clinical algorithm and/or blood test panel that successfully highlights patients at a high risk of developing irAE, prior to commencing therapy. This would allow closer monitoring of high-risk patients, leading to earlier diagnosis of irAE. Currently irAE can be tricky to diagnose and have overlapping symptoms with the malignancy and related concomitant treatments (27). Earlier diagnosis would lead to reduced hospitalisation, better outcomes, and reduced

BIO-CHECKPOINT

interruptions to the anti-cancer therapy, which may lead to better malignancy curative rates. There is also a potential to reduce morbidity and mortality risk for this subset of patients, as well as an overall reduction in resource burden.

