4.4 STUDY PROCEDURES

Please refer to the flow chart on page viii for a summary of the study procedures. The study procedures described below will be conducted in accordance with SOPs and/or work instructions provided by the CI.

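### Does the exclusion for an existing cancer contradict a cohort made up entirely of cancer patients?

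*Combined protocol and SAP*

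**What the plan says.** Section 4.2 of the protocol includes adult oncology patients prescribed one of seven named ICPIs, and adds "All cancer subtypes are included". Its exclusion list contains "Those with a pre-existing malignancy", with no qualifier and no look-back period. Two neighbouring exclusions concern medical history; one of them reads "Those with a previous medical history of autoimmune disease", and the other covers endocrine disease in similar terms.

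Section 5.1 describes how the lists are used: "Patients who are yet to start ICPI will be listed in a password protected sheet with the expected day of their chemo". The lead researcher then checks "if the patients listed meet the inclusion criteria and if they have any of the features of the exclusion criteria", and "Those that meet the exclusion criteria will be deleted off the list".

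Section 4.4 points to further material: "Please refer to the flow chart on page viii for a summary of the study procedures". It also refers to standard operating procedures or work instructions. Neither the flow chart nor those procedures could be read for this review.

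**The concern.** An inclusion criterion that requires cancer and an exclusion criterion that forbids it, in the same section and applied to the same people, look irreconcilable. Screening takes place before the first ICPI dose, and by then every candidate has a malignancy that already exists.

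The protocol's vocabulary seems to make matters worse. The neighbouring history exclusions say that they concern the past, and this one does not. Where the word *malignancy* appears elsewhere, in section 3.3, it means the cancer under treatment, as in "overlapping symptoms with the malignancy and related concomitant treatments".

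If the term were truly undefined in use, patients with recurrent disease, two cancers or an old cured cancer might be admitted or refused inconsistently. A reader of the published results could not then tell whom the cohort represents.

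**Working it through.** The protocol states no figure for this criterion, so there is none to reproduce. The check is a comparison of the sections, with one short calculation.

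**1. The literal reading.** Candidates are oncology patients already prescribed an ICPI (sections 4.1 and 5.1), so all of them have cancer at screening. If any cancer present before the ICPI excludes, the number eligible is 0. Section 7.0 expects about 120 patients and wants at least 47. The protocol's own recruitment plan therefore rules this reading out.

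**2. The reading that fits.** *Pre-existing* needs a reference point. If that point is the start of the ICPI, the result is step 1. If it is the cancer for which the ICPI is prescribed, the criterion becomes an exclusion for another or earlier cancer, which sits naturally beside the autoimmune and endocrine history items. The statement that all cancer subtypes are included concerns type of cancer, not cancer history, and is compatible with this. The uses of *malignancy* in section 3.3 are narrative about symptoms and cure; they do not define an eligibility term.

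**3. How much stays open.** The following patient types and readings are illustrative and are not taken from the protocol.

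| Reading of the exclusion | First presentation, single cancer | Recurrence of treated cancer | Second primary at the same time | Remote cured different cancer | Types admitted |
|---|---|---|---|---|---|
| Literal: any cancer before ICPI | no | no | no | no | 0 of 4 |
| A: any cancer other than the treated one, past or current | yes | yes | no | no | 2 of 4 |
| B: any earlier cancer episode, including the same cancer | yes | no | yes | no | 2 of 4 |
| C: another cancer still active at ICPI start | yes | yes | no | yes | 3 of 4 |

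Readings A, B and C admit different sets, and only a first presentation of a single cancer is admitted under all three. The table counts types, not patients. It shows that the phrase can be parsed in several ways; it does not show that anyone would be misclassified.

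**4. Who applies it, and when.** Section 5.1 gives the check to one lead researcher, and section 4.2 restricts the study to one hospital's oncology patients. Divergent readings between sites cannot arise, and divergence between screeners is unlikely. Screening precedes the ICPI, and so precedes any immune-related adverse event (irAE). Section 3.1 compares patients within the cohort who do and do not develop an irAE. The choice among A, B and C changes whom that comparison describes, but cannot be steered by its outcome.

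**5. Room in the sample size.** Using only the figures in section 7.0, the expected number exceeds the stated minimum by 120 − 47 = 73 patients, and 73 / 120 = 0.608. Losses from every cause combined would have to reach about 61% before recruitment fell below 47. Section 7.0 does not say whether 120 is already net of the exclusions. The 47 is taken at face value here, because that section states no effect size against which to check it.

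**The case for a change.** The best case for amending the text is reproducibility. Rejecting the literal reading does not select one of the others, and section 7.0 defines the cohort as first-time ICPI patients who escape the exclusions, so this phrase helps to set the study population. The gap may also be awkward to close afterwards: the analysis sheet described in section 4.1 holds cancer type but no field for recurrence or a second cancer, and section 5.1 has excluded patients deleted without mentioning a recorded reason. Section 15.0 plans publication, and the phrase alone would not tell a reader who was left out. A clarification would take a sentence or two.

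Part of this stands. The wording is loose, and section 4.2 does not settle the three borderline groups. But the point concerns description. The person who applies the criterion will know the rule used and can state it in the report. The flow chart or operating procedures may already contain a definition, and their absence from the text available here is no evidence that the study lacks one. Nothing in the documents shows a bias, an altered comparison or a shortage of patients arising from the choice of reading, and samples, assays and analysis would be the same after an amendment.

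**Conclusion.** The concern does not call for a change. Section 4.2 contradicts itself only on a reading that would leave no eligible patients and that no screener would adopt. On any workable reading, the exclusion refers to a cancer other than, or earlier than, the one being treated, and recruitment is not blocked.

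What remains is missing detail about recurrence, concurrent second primaries and remote cured cancers. Its size in patients is unknown, because the documents give no frequencies for these groups.

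This conclusion assumes that the lead researcher carries out the eligibility check as section 5.1 describes, before treatment and with one consistent reading, and that the rule used can be reported with the results. If several people screened with different readings, the description of the cohort would be less certain. The assessment of irAE outcomes and the comparison in section 3.1 would still be made in the same way.
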